3.0 Objectives

- The purpose of this study is to determine the safety of HF-LED-RL phototherapy in Fitzpatrick skin types I to III.
- We hypothesize that HF-LED-RL phototherapy at fluences of 480 J/cm² may be safe in subjects with Fitzpatrick skin types I to III. We hypothesize that HF-LED-RL phototherapy at fluence of 640 J/cm² may be safe in subjects with Fitzpatrick skin types I to III.

5.0 Study Procedures

5.1 Study Design

- This is a single-blind, randomized, ascending dose escalation Phase I study of HF-LED-RL in healthy subjects with Fitzpatrick skin types I to III to evaluate safety of HF-LED-RL in Fitzpatrick skin types I to III (Figure 1). The study endpoint of 640 J/cm² is due to feasibility, as this dose corresponds to two hours of HF-LED-RL irradiation, and we anticipate decreased subject compliance with HF-LED-RL exposures longer than 2 hours in duration. The study endpoint of 640 J/cm² was also selected as this dose demonstrated increased anti-fibrotic properties in vitro compared to lower doses of HF-LED-RL (Mamalis 2015). Subjects will receive HF-LED-RL phototherapy or mock therapy three times a week for

three consecutive weeks, which is a standard phototherapy regimen based on phototherapy guidelines (Anderson et al 2015, Menter et al 2010, Zanolli et al 2004).

The HF-LED-RL light source is a commercially available Omnilux New-U hand-held LED-RL phototherapy unit (provided by Photo Therapeutics, Carlsbad, CA, USA), and is FDA-cleared for treatment of periorbital rhytides (crow's feet) with doses up to 160 J/cm². The temperature-matched mock therapy unit, also provided by Photo Therapeutics, Carlsbad, CA, USA, generates only heat output comparable to heat generated by the HF-LED-RL device, which is less than two degrees Celsius of heat output, and does not emit HF-LED-RL.

We do not classify erythema (redness) lasting less than 24 hours as an adverse event in our study, and is expected to occur in at least 10% of subjects as previously demonstrated in published studies (Sadick 2008, Sadick 2008). Common expected procedure outcomes include: warmth, erythema (redness), and edema (swelling) that is expected to last less than 24 hours.

- The maximum tolerated dose (MTD) is defined as the dose level below the dose producing unacceptable but reversible toxicity in two or more subjects ($\geq 20\%$) and is considered the upper limit of subject tolerance. If two or more subjects experiences any adverse event (including: first-degree or higher skin burning or blistering, erythema lasting more than 24 hours, swelling, pain, ulceration, infection, change in sensation, and/or

muscle weakness), then this is the dose one above the MTD and we will not proceed with this dose or escalate the dose. The dose below the dose that generated the adverse event is the MTD. Rare but serious adverse events include second or higher degree skin burn, severe swelling, pain, ulceration, change in sensation, or muscle weakness leading to hospitalization, life-threatening events, or death.

The data safety monitoring board (DSMB) includes: [name], [name], and [name]

HF-LED-RL phototherapy and mock therapy at fluences of 480 J/cm² or 640 J/cm² will be administered to 65 subjects with Caucasian (white) skin types (Fitzpatrick skin types I, II, and III) to determine safety of HF-LED-RL at fluences of 480 J/cm² and 640 J/cm² in Fitzpatrick skin types I, II, and III. Because up to 320 J/cm² HF-LED-RL was found to be safe in all Fitzpatrick skin types (unpublished data from “previous Phase 1 LED-RL study”), this study will study 480 J/cm² and 640 J/cm² in Fitzpatrick skin types I, II, and III based on Spilker’s dose escalation protocol (X=160 J/cm², 2X=320 J/cm², 3X = 480 J/cm², and 4X = 640 J/cm²).

Number of subjects in each group:

Group 1 (480 J/cm²; 3 or 6 HF-LED-RL phototherapy subjects and 2 or 4 mock therapy subjects) - Total 5 or 10 subjects

Group 2 (640 J/cm²; 3 or 6 HF-LED-RL phototherapy subjects and 2 or 4 mock therapy subjects) - Total 5 or 10 subjects

Group 3 (480 or 640 J/cm² depending on dose escalation algorithm; 27 HF-LED-RL phototherapy subjects and 18 mock therapy subjects) - Total 45 subjects

* If there is one adverse event in one subject in either Group 1 or 2, five additional subjects will be added to that group (3 will receive HF-LED-RL and 2 will receive mock therapy).

We based our dose escalation protocol for this new study on a similar Phase 1 dose escalation study design outlined in the Journal of National Cancer Institute (Le Tourneau et al 2009), to determine dose escalation and to account for a possible outlier effect in the treatment group. Dose escalation starts at fluence of 480 J/cm² and continues up to fluence of 640 J/cm² until at least two subjects among a cohort of five to ten subjects experience an adverse event (i.e. $\geq 20\%$ of subjects with an adverse event at that dose level).

Our dose-escalation protocol is as follows (Figure 2): In the first group (Group 1), HF-LED-RL phototherapy or mock therapy treatment time durations associated with 480 J/cm² will be administered to five subjects. Five subjects will be enrolled with three subjects randomized to HF-LED-RL phototherapy and two subjects randomized to mock therapy. Randomization is performed with website: www.randomizer.org. The randomizer will generate arabic numerals (e.g. “1”, “2,” “3”). Each enrolled subject will undergo two randomizations. For the first randomization, “1” is Group 1, “2” is “Group 2” and “3” is Group 3. 10 subjects will be

randomized to Group 1, 10 subjects will be randomized to Group 2, and 45 subjects will be randomized to Group 3. If there are no adverse events in the first five subjects of either Group 1 or 2, then the remaining 5 subjects of the 10 subjects randomized to that group will default into Group 3. For the second randomization, "1" is HF-LED-RL phototherapy and "2" is mock therapy. This study is single-blind and subjects will be blinded to this randomization, while researchers ([name], [name], and [name]) have knowledge of all subjects' randomization for the entirety of this study.

Dose escalation starts at fluence of 480 J/cm² and continues up to fluence of 640 J/cm² until at least two subjects among a cohort of five to ten subjects experience an adverse event (i.e. >20% of subjects with an adverse event at that dose level). If there are no adverse events in the five subjects treated with HF-LED-RL or mock therapy at fluence of 480 J/cm² in Group 1, then we will escalate the dose of HF-LED-RL or mock therapy to fluence of 640 J/cm² in the next cohort of five subjects (Group 2). If there is a single adverse event with HF-LED-RL or mock therapy at fluence of 480 J/cm², we will repeat the same dose of 480 J/cm² in a new cohort of five additional subjects (Group 1A). This is to account for a possible outlier effect. If two or more subjects in the first cohort of Group 1 experiences an adverse event with HF-LED-RL or mock therapy at fluence of 480 J/cm², then the study will stop and the MTD is 320 J/cm². If there are no adverse events in Group 1A, then the dose will be escalated to 640

J/cm2 in the next cohort (Group 2). If there is an adverse event in Group 1A ($\geq 20\%$), then the study will stop and the MTD is 320 J/cm2.

After either a MTD has been established or the study endpoint of 640 J/cm2 has been achieved, an additional 27 HF-LED-RL phototherapy subjects (for a total of 30 or 33) and 18 mock therapy (for a total of 20 or 22) (determined randomly) will be enrolled to satisfy Hanley's Rule of Three, such that it can be concluded with 95% confidence that fewer than 1 person in 10 will experience an adverse event (Figure 3). (Hanley 1983) If the MTD is 320 J/cm2, then the study will be stopped and no further testing of the MTD of 320 J/cm2 in the larger cohort will be indicated because the MTD of 320 J/cm2 was already tested in a large cohort in the "previous Phase 1 LED-RL study". Of the larger expansion cohort, the study will be halted (stopped) if adverse events determined to be device related equals or exceeds 30%.

This clinical trial will be registered on <https://clinicaltrials.gov> following IRB approval and prior to subject enrollment.

- The subject will receive standard of care treatment in the dermatology clinic for any adverse event. Physical examination/visual inspection of the treated forearm will occur at every study visit. Treatment will be initiated, if indicated, for any procedural outcomes or adverse events noted at every study visit. Any general dermatology adverse events will be managed by [name] in the Dermatology clinic, per standard of care. If a skin ulcer occurs, we will record the skin ulceration as a superficial ulceration

(meaning it is nearly flush with the skin) or, if measurable, the depth of ulceration in millimeters. If skin ulceration occurs, we will consult [name], who is an expert in wound healing and head of the Sacramento VA wound clinic, for management. If change in sensation or muscle weakness occurs in a subject, the subject will be sent to Sacramento VA Emergency Room for urgent grading and management. If there are any other adverse events that cannot be managed in the Dermatology clinic, the subject will be sent to the Sacramento VA Emergency Room for urgent care.

- All procedures will occur in the Dermatology clinic at the Sacramento VA Medical Center (observed by [name], [name], and/or [name]), three times per week for three consecutive weeks for total of nine study visits. Subjects will be counseled regarding common expected procedure outcomes including warmth, erythema (redness) and edema (swelling), found to resolve within 24 hours in other studies. (Sadick 2008) Any adverse events that occur in office during or immediately after HF-LED-RL phototherapy or mock therapy session will be recorded by [name]. Subjects will be called on Mondays to serve as a reminder of upcoming study visits for the week.
- Subjects will record daily any adverse events that occur at home using a subject diary of adverse events. The study diary will be completed approximately every 24 hours from the time of completion of the study procedure. The subject diary will have instructions on the first page and a

chart on other pages for the subject to complete for every symptom noted at home (attached as separate document). The chart will have headers of 'Date,' 'Time Symptom Started,' 'Time Symptom Cleared,' 'Location,' 'Describe the Symptom,' 'Severity,' 'Things that Make it Better,' 'Things that Make it Worse,' 'Any Treatments Tried at Home,' and 'MD Initial'. If a subject notices any changes sooner than 24 hours, they are encouraged to note it in their subject diary as soon as possible. If there are no changes, subjects will write "There are no changes." Recording in a diary should take 0 minutes per day if there is no reportable change. It may take up to 3 minutes per day if there is a reportable change. If there are any reportable changes, subjects will describe reportable changes using the provided instructions and template. Prior to study procedure at every study visit, subjects will be asked about any adverse events that have occurred, including, but not limited to: erythema, blisters, swelling, pain, ulceration, infection, numbness, tingling, and weakness. Subject's diaries will also be reviewed prior to study procedure at every study visit. [name], [name], or [name] will initial in the 'MD Initial' area at every visit, certifying that one of the researchers has reviewed the subject diary at every study visit.

Study Timeline:

HF-LED-RL Phototherapy or mock therapy procedure times are as follows:

Group 1 (480 J/cm²; 3 or 6 HF-LED-RL phototherapy subjects and 2 or 4 mock therapy subjects) - 90 minutes

Group 2 (640 J/cm²; 3 or 6 HF-LED-RL phototherapy subjects and 2 or 4 mock therapy subjects) - 120 minutes

Group 3 (480 J/cm² or 640 J/cm² based on dose escalation algorithm; 27 HF-LED-RL phototherapy subjects and 18 mock therapy subjects) – 90 or 120 minutes

* If there is one adverse event in one subject in either Group 1 or 2, five additional subjects will be added to that group (3 will receive HF-LED-RL and 2 will receive mock therapy).

Sample Timeline *Please see above list for procedure times for Groups 1, 2, and 3.

Week 0: (All subjects will be tested for photosensitivity with 20 minutes and 106.7 J/cm² of HF-LED-RL)

Visit 1

Screening and obtaining informed consent (10 minutes) Subject can return at a later date to sign the informed consent if he or she desires to review the consent form in more detail.

Physical examination of nondominant forearm, pre-procedure photograph (5 minutes)

Procedure for testing photosensitivity – HF-LED-RL phototherapy on nondominant upper forearm (20 minutes, 106.7 J/cm²)

Post-procedure photograph (5 minutes)

Visit 2 (24 hours after Visit 1)

Physical examination of nondominant forearm for photosensitivity which includes warmth, erythema (redness), edema (swelling), rash, pain, sensory changes, muscle weakness, or discomfort lasting more than 24 hours (10 minutes)

Photograph (5 minutes)

Subjects who are photosensitive will be excluded from this study. Subjects who are not photosensitive will proceed with study protocol.

Week 1:

Monday (Visit 3)

Physical examination of nondominant forearm, pre-procedure photograph (5 minutes)

Procedure (Refer to above for procedure duration)

Post-procedure photograph (5 minutes)

Wednesday (Visit 4)

Physical examination of nondominant forearm, pre-procedure photograph, and review of subject diary of adverse events (5 minutes)

Procedure (Refer to above for procedure duration)

Post-procedure photograph (5 minutes)

Friday (Visit 5)

Physical examination of nondominant forearm, pre-procedure photograph, and review of subject diary of adverse events (5 minutes)

Procedure (Refer to above for procedure duration)
Post-procedure photograph (5 minutes)

Week 2:

Monday (Visit 6)

Physical examination of nondominant forearm, pre-procedure photograph, and review of subject diary of adverse events (5 minutes)

Procedure (Refer to above for procedure duration)
Post-procedure photograph (5 minutes)

Wednesday (Visit 7)

Physical examination of nondominant forearm, pre-procedure photograph, and review of subject diary of adverse events (5 minutes)

Procedure (Refer to above for procedure duration)
Post-procedure photograph (5 minutes)

Friday (Visit 8)

Physical examination of nondominant forearm, pre-procedure photograph, and review of subject diary of adverse events (5 minutes)

Procedure (Refer to above for procedure duration)
Post-procedure photograph (5 minutes)

Week 3:

Monday (Visit 9)

Physical examination of nondominant forearm, pre-procedure photograph, and review of subject diary of adverse events (5 minutes)

Procedure (Refer to above for procedure duration)
Post-procedure photograph (5 minutes)

Wednesday (Visit 10)

Physical examination of nondominant forearm, pre-procedure photograph, and review of subject diary of adverse events (5 minutes)

Procedure (Refer to above for procedure duration)
Post-procedure photograph (5 minutes)

Friday (Visit 11)

Physical examination of nondominant forearm, pre-procedure photograph, and review of subject diary of adverse events (5 minutes)

Procedure (Refer to above for procedure duration)
Post-procedure photograph (5 minutes)

Average length of study visits for: Group 1 - 100 minutes, Group 2 - 130 minutes, Group 3 – 100 or 130 minutes based on dose escalation algorithm.

Detailed Procedure: Intervention — Subject will be inside a private clinic exam room. The subject's nondominant proximal anterior forearm will be examined and cleaned with alcohol pads. A surgical marking pen will be used to mark three points to outline the procedure area at the start and completion of every session to ensure reproducible placement of the device. The HF-LED-RL phototherapy or mock therapy hand-held unit will be held in place and in direct contact with the cleaned area using non-adhesive tape (ACE elastic bandage or similar) during the procedure. Protective eyewear will be provided for all subjects to use at HF-LED-RL phototherapy and mock therapy sessions. [name], [name], or [name] will be observing the procedure and assessing for any safety issues during and immediately post-procedure. Treatment will be started, if indicated, for any adverse events noted during physical examination at each study visit.

[figure not shown]

Figure 1. Schematic of study design.

[figure not shown]

Figure 2. Dose escalation algorithm.

Group 3: Expansion cohort of maximally tolerated dose or study endpoint
Three study visits per week for three consecutive weeks

[figure not shown]

Figure 3. Expansion cohort design.

- Subjects who receive HF-LED-RL phototherapy may have a greater risk compared to subjects who receive mock therapy. However, all subjects are closely monitored by [name], [name], and/or [name] three times per week for three consecutive weeks at each study visit and by review of subject's diary of adverse events. All safety precautions, including sanitizing equipment and goggles with Sani-Wipe before each study subject use, requiring subjects to use safety goggles during each session, and verifying subject identity, study procedure site of left or right forearm, and correct dose of HF-LED-RL or mock therapy, will be taken. All adverse events will be documented and if necessary, reported to the IRB.

All HF-LED-RL phototherapy and mock therapy hand-held units will be cleaned with anti-germicidal wipes before and after each procedure. All subjects' nondominant proximal anterior forearm will be cleaned with alcohol wipes prior to placement of HF-LED-RL phototherapy or mock therapy unit. All subjects will be provided with protective eyewear during all procedures. The study procedure will occur on the subject's nondominant proximal anterior forearm, with a surgical marking pen to mark three points to outline the procedure area at the start and completion of every session to ensure reproducible placement of the device. Subjects will be asked which hand is dominant or preferred when writing. Subjects can report being left-handed, right-handed, or ambidextrous. Subjects who are ambidextrous may identify their preferred nondominant forearm for the

study procedure to Principal Investigator ([name]) or study coordinators ([name] and [name]) prior to start of study.

In addition to the aforementioned precautions to minimize risks, all subjects will be screened by [name], [name], and/or [name] by reviewing their medical records and performing a physical examination after obtaining informed consent. [name], [name], and/or [name] will be present during HF-LED-RL phototherapy or mock therapy procedures, and observe and document any common expected procedure outcomes and adverse events. Any adverse event experienced by the subject will be evaluated and treated according to the standard of care.

The study subjects have direct contact information (phone numbers and email addresses) of [name], and [name] may be reached at any time.

The Omnilux New-U hand-held HF-LED-RL phototherapy unit is commercially available and FDA-cleared for treatment of periorbital rhytides (crow's feet) with doses up to 160 J/cm². We do not expect the risk of using HF-LED-RL phototherapy or mock therapy in our current study will be any different from the current FDA-cleared indication.

- Potential subjects will be recruited from the Sacramento VA Medical Center, Mather, and any subjects who are willing and eligible for the study will be invited to participate. The total number of participants approved for recruitment is 200.

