5.5 Study Evaluations

- All subjects will be evaluated for photosensitivity (20 minutes with fluence of 106.7 J/cm² of HF-LED-RL) prior to start of study procedures, as recommended by the manufacturer's user guide instructions. A 20-minute session of HF-LED-RL phototherapy will be performed on the subject's nondominant proximal anterior forearm, and evaluation for photosensitivity will occur 24 hours post HF-LED-RL phototherapy. Subjects will be excluded from the study if they fail the 20 minute photosensitivity evaluation or do not return for photosensitivity evaluation between 24-48 hours post HF-LED-RL photosensitivity testing. Criteria for failing the photosensitivity testing include but are not limited to: warmth, erythema (redness), edema (swelling), rash, pain, or discomfort lasting more than 24 hours. Subjects are required to complete a study diary and report any adverse events to [name], [name], or [name].

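### Subjects are said to be blinded, but no feature of the plan is stated to conceal the light, which every subject receives in Week 0 and the mock unit lacks

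*Combined protocol and SAP*

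**What the plan says.** Section 5.1 (Study Design) states: "This study is single-blind and subjects will be blinded to this randomization". The named researchers, by contrast, know every subject's "randomization for the entirety of this study". Subjects are therefore the only party said to be blinded.

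The mock unit "generates only heat output comparable to heat generated by the HF-LED-RL device", "and does not emit HF-LED-RL". It is described as temperature-matched. No visual match or dummy light is described.

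The Sample Timeline in Section 5.1 gives everyone the active unit first: "All subjects will be tested for photosensitivity with 20 minutes and 106.7 J/cm² of HF-LED-RL". Section 5.5 (Study Evaluations) confirms this and places the test on the arm used for the study: "A 20-minute session of HF-LED-RL phototherapy will be performed on the subject's nondominant proximal anterior forearm".

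On anything that might hide the light, the Detailed Procedure says: "Protective eyewear will be provided for all subjects to use at HF-LED-RL phototherapy and mock therapy sessions". The later list of safety precautions requires goggles in each session. The unit is held against the skin with an elastic bandage or similar. The eyewear is presented as protection and the bandage as a way of keeping the unit in place.

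Subjects record adverse events at home in a daily diary (Section 5.1). Section 5.6 (Data Analysis) plans adverse event frequency by HF-LED-RL and mock group, and mean and total erythema duration, with duration taken from the diary. Section 2.0 (Introduction) gives the purpose of the mock: to help tell effects of the light from effects of the heat.

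**The concern.** A subject blind needs the two units to be indistinguishable to the subject, or the difference to be hidden. The plan matches heat but not light, and describes no means of hiding the light. Week 0 then gives every subject a reference session with the active unit. If the light is visible, a mock subject can notice at the first treatment session that it is missing, and an active subject can notice that it is still there.

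What is at stake is the comparison the mock exists to support. Section 2.0 reads an event seen only with the active unit as possibly due to light, and one seen with both as possibly due to heat. If subjects who know their arm report pain, altered sensation or persisting redness differently, the pattern of events across arms reflects reporting as well as exposure. The clinic team cannot restore the blind, because the people who question subjects, review diaries and examine the arm know the allocation.

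**Working it through.** **Step 1. Is Week 0 a fair preview of an active session?** Inputs, all from Section 5.1: 106.7 J/cm² in 20 minutes (Week 0), 480 J/cm² in 90 minutes, 640 J/cm² in 120 minutes. Output is fluence divided by time.

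- Week 0: 106.7 / 20 = 5.335 J/cm² per minute
- 480 J/cm²: 480 / 90 = 5.333
- 640 J/cm²: 640 / 120 = 5.333

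The plan's Week 0 fluence reproduces from the treatment rate: 20 × 480 / 90 = 106.67, which rounds to 106.7. The test runs at the same output, on the same forearm, as an active session.

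**Step 2. What does each arm receive afterwards?** Visits 3 to 11 are nine sessions, which is 9 × 90 = 810 minutes (13.5 hours) or 9 × 120 = 1,080 minutes (18 hours).

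| | Week 0 | Nine sessions |
|---|---|---|
| Active arm | light and heat | light and heat |
| Mock arm | light and heat | heat only |

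The mock arm changes unit after Week 0 and the active arm does not.

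**Step 3. Is anything stated to hide that change?** Eyewear: stated purpose is protection; opacity not given. Bandage and skin contact: stated purpose is placement; light leakage not given. Cover, drape or screen: none described. Check of the blind: none described. Whether the light is visible cannot be settled from the text.

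**Step 4. Which outcomes are exposed?** Pain and change in sensation rest on the subject's report. Erythema counts as an adverse event when it lasts more than 24 hours, but visits fall on Monday, Wednesday and Friday, 48 or 72 hours apart. Redness that clears between 24 hours and the next visit is timed only by the diary. Blistering or ulceration can be seen at examination and in photographs.

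**Step 5. What is not exposed?** The sample size of 30 active subjects follows from the Rule of Three: 3 / 30 = 0.10. The exact one-sided 95% limit for no events is 1 − 0.05^(1/30) = 0.0950. Neither formula contains mock data.

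**Step 6. Illustration of the bias, on assumed values.** Let both arms have true event rate p, and let mock subjects who recognise their unit report a fraction r of their events. The false difference is p(1 − r). Neither p nor r is in the documents.

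| p | r = 1 | r = 0.75 | r = 0.5 |
|---|---|---|---|
| 10% | 0 points | 2.5 points | 5 points |
| 30% | 0 points | 7.5 points | 15 points |

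With 20 mock subjects, r = 0.5 turns 2 expected reports into 1 at p = 10%, and 6 into 3 at p = 30%. This shows only how the error scales. It is not an estimate for this trial.

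**The case against.** The strongest reply is that silence is not failure. The unit lies against the skin under a bandage and the subject wears goggles, so the light may in practice be out of sight. That stands. A reader might infer that the blind is likely to fail, or that all 20 or 22 mock subjects would recognise their arm. The documents do not support either: visibility is not described, and 20 or 22 is the plan's count for the mock arm, not an estimate of how many would guess.

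A reader might also infer that lost blinding threatens the claim of fewer than 1 in 10, because one event in 30 raises the exact upper limit from 9.5% to 14.9%. That limit uses active-arm events only, so mock subjects recognising the mock cannot move it. It would move only if active subjects changed their own reporting, and the documents give no basis for assuming or sizing that.

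The reach is limited in other ways. Escalation counts events in either arm together, so it makes no between-arm contrast; lost blinding touches it only if a countable event is reported, or not reported, because of it. Section 5.6 plans frequencies and durations and no between-arm test. Section 2.0 words its attribution cautiously. Sessions are observed, and each treatment visit has an examination and photographs. The examiners are unblinded, but a photograph does not change with what the subject believes.

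What remains is that the plan as written supplies the reference session, supplies a mock without the light, and names nothing that stands between the two.

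**Conclusion.** The point holds as a gap in the design. Subject blinding is stated without any described means of concealing the one feature that distinguishes the units, after every subject has had a session with that feature present. If the light is visible, the active-versus-mock comparison of pain, change in sensation and diary erythema duration is open to reporting bias, and so is the light-versus-heat attribution drawn from it. This rests on one assumption that the documents neither confirm nor exclude: that subjects can see the light, or its absence, during sessions.

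The size cannot be derived from the documents. The single-arm zero-event bound is unaffected by mock recognition, and visit examinations and photographs are less exposed. The matter should be settled before enrolment, because concealment cannot be added once the data are collected. If the sponsor already conceals the light, stating how in the protocol answers the main point.

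**What to change.** Conceal the light in the same way in both arms and in the Week 0 test, with the concealment in place before switch-on and removed after switch-off. Three means would serve:

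- opaque eyewear;
- a drape or screen that blocks the subject's view;
- an opaque cover over the unit, but only after confirming on both units that the stated heat match (less than two degrees Celsius) still holds, since a cover could alter heat loss and the control depends on that match.

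State the chosen means in the Detailed Procedure of Section 5.1. At Visit 11, ask each subject which unit they think they had, and add a tabulation of the guesses by arm to Section 5.6. If concealment is not feasible, describe the subject-reported between-arm comparisons as potentially unblinded.

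The cost is minor discomfort and set-up time over sessions of 90 to 120 minutes, one question at the last visit, and a temperature check if a cover is used. Dose, schedule, sample size and stopping rules are unchanged.
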